#### **9.4.5 Adherence and Retention Analyses**

N/A

#### **9.4.6 Baseline Descriptive Statistics**

Addressed in general approach.

#### **9.4.7 Planned Interim Analysis**

An interim analysis of all endpoints will be performed after the first 10 patients treated with HBOT complete the study compared to matched cohort of 30 patients from case review.

##### **9.4.7.1 Safety Review**

Administration of study device will be halted in the event of the following:

CONFIDENTIAL

This material is the property of the NYU School of Medicine and Langone Medical Center. Do not disclose or use except as authorized in writing by the study sponsor

Interventional Template Version: 11 January 2019

- If the study team deems that transport or treatment of patients in the hyperbaric unit significantly increases the risk of respiratory failure
- If any patient experiences a death which is likely to be attributable to the use of HOBT.

It is the responsibility of the co-Principal Investigators to oversee the safety of the study at his/her site. This safety monitoring will include careful assessment and appropriate reporting of adverse events as noted above, as well as the construction and implementation of a site data and safety-monitoring plan. Medical monitoring will include a regular assessment of the number and type of serious adverse events.

Safety oversight will be under the direction of the co-Principal Investigators and co-Investigators. After the first 10 patients complete the protocol, a pause in enrollment will be initiated and the data will be reviewed to ensure all adverse events were reviewed.

The investigators will meet after 10, 20, and 40 patients complete the protocol to assess safety and efficacy data on each arm of the study. Events that will be monitored are 1. need for mechanical ventilation 2. upgrade in level of care 3. seizure activity and 4. death.

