#### 2.2.2 *Clinical Data to Date*

HBOT is an FDA cleared treatment that has been used as the primary treatment for Decompression Sickness and Carbon monoxide poisoning and adjunctive treatment for a multitude of disease states. Its mechanism of action is to reverse local tissue hypoxia, promote angiogenesis, increase circulating

CONFIDENTIAL

This material is the property of the NYU School of Medicine and Langone Medical Center. Do not disclose or use except as authorized in writing by the study sponsor

Interventional Template Version: 11 January 2019

stem cells, reduce edema and blunt the inflammatory immune response. It has been used for over 50 years and has an excellent safety profile. There is no contraindication for treating patients with viral pneumonia and the only absolute contraindication would be an untreated pneumothorax. The rationale for using HBOT to treat COVID-19 respiratory distress is based on the pure hypoxia with an increase in inflammatory markers including D-dimer, Lymphocytes, IL-6, Ferritin, LDH, and CRP. To our knowledge, the only cases that have been performed thus far are preliminary cases in Wuhan, Italy and potentially South Korea in patients with severe respiratory distress. These patients have shown clinical objective improvement in symptoms and on re-examination of imaging. At this time, it is available as non-peer reviewed data (see attachment).

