### **2.4 Potential Risks & Benefits**

#### **2.4.1 Known Potential Risks**

##### Risks Associated with Hyperbaric Therapy:

The risks of hyperbaric oxygen are well reported. Hyperbaric oxygenation typically requires constant care and may be difficult for individuals experiencing nausea or vomiting, claustrophobia, or altered mental status from lack of oxygen. The most common side effects that you may feel, because of the high pressure and small space, include fatigue, lightheadedness, anxiety or claustrophobia, and ear discomfort which can be a pain and a “popping” feeling. More severe side effects include fluid buildup of the middle ear, sinus damage, trauma from the increased air pressure (baurotrauma), change in vision, oxygen toxicity seizures, and development of collapsed lungs (pneumothorax). Development of a pneumothorax may result in cardiopulmonary collapse, and ultimately death. However, patients will be instructed on how to prevent these side effects and the oxygen dose given to participants will be determined specifically by healthcare providers who will take into consideration participants' overall health and age to reduce complications.

There also exists the risk of recurrence of symptoms after exiting from the chamber. Furthermore, there exists the risk of cross contamination/exposure of other strains of COVID-19, however all the chambers will be set up specifically for COVID-19 positive patients and will be thoroughly cleaned after used in order to reduce risk of cross-contamination. Due to the oxygen rich environment there is an increased inherent fire risk. Due to the novelty of COVID-19, the risks of hyperbaric oxygen specifically for COVID-19 patients are currently unknown.

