#### **4.2.3 Safety Endpoints**

We will collect all adverse events (AE), including severe adverse events (SAEs) for the study. For AEs potentially related to HBOT we will consider otic barotrauma, myopia, oxygen toxicity seizures and acute pulmonary edema. For each patient we will count the total number of AEs and SAEs during hospitalization.

CONFIDENTIAL

This material is the property of the NYU School of Medicine and Langone Medical Center. Do not disclose or use except as authorized in writing by the study sponsor

Interventional Template Version: 11 January 2019

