#### **9.4.4 Safety Analyses**

To assess severe adverse events (SAEs), we will consider otic barotrauma, myopia, oxygen toxicity seizures and acute pulmonary edema. For each patient we will count the total number of SAEs during hospitalization.

SAEs will be summarized by computing mean and standard deviation for each comparison group. We will further compare mean number of SAEs between HBOT and SOC groups using linear regression. The outcome will be log transformed to account for the potential violation of normality. We will report difference in mean along with 95% confidence interval around the mean.

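### Pneumothorax, which section 2.4.1 calls a possibly fatal HBOT risk, is not tallied as its own event at the planned reviews and, read literally, is left out of the SAE comparison in 9.4.4

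*Combined protocol and SAP*

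**What the plan says.** Section 2.4.1 (Known Potential Risks) places pneumothorax among the more severe side effects of HBOT and spells out the outcome: "Development of a pneumothorax may result in cardiopulmonary collapse, and ultimately death". Section 2.2.2 says that "the only absolute contraindication would be an untreated pneumothorax", and sections 5.1 and 5.2 screen for it at entry.

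After eligibility, the named lists do not mention it. Section 4.2.3 (Safety Endpoints) says: "For AEs potentially related to HBOT we will consider otic barotrauma, myopia, oxygen toxicity seizures and acute pulmonary edema". Section 8.1 repeats those four events. Section 9.4.4 (Safety Analyses) uses the same four for a different purpose: "To assess severe adverse events (SAEs), we will consider otic barotrauma, myopia, oxygen toxicity seizures and acute pulmonary edema". It then compares the mean SAE count between the HBOT and SOC groups.

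On review times, section 9.4.7.1 says: "The investigators will meet after 10, 20, and 40 patients complete the protocol to assess safety and efficacy data on each arm of the study". It then names what is watched: "Events that will be monitored are 1. need for mechanical ventilation 2. upgrade in level of care 3. seizure activity and 4. death". The Data Safety Monitoring Plan in 8.12 carries the same text.

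The plan also has general provisions that are not tied to any list. Section 4.2.3 opens with "We will collect all adverse events (AE), including severe adverse events (SAEs) for the study". Section 8.6 requires every AE to be documented whatever its relationship to treatment. Sections 8.12 and 9.4.7.1 call for regular review of SAEs by number and type, and for a check on all AEs at the enrolment pause after 10 patients.

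**The concern.** Pneumothorax is the only HBOT complication for which 2.4.1 describes a fatal course. Other risks from that section, namely ear barotrauma, visual change and seizures, have counterparts in the event lists. Pneumothorax has none.

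Two things are at stake.

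- **Visibility at the reviews.** All enrolled patients are in respiratory distress from COVID-19. Ventilation, escalation of care and death are expected disease outcomes. A pneumothorax that reaches the reviewers only under one of those labels is hard to separate from progression. The halting criteria in 8.11 depend on judging whether a death is attributable to HBOT, or whether treatment has raised the risk of respiratory failure. Those judgements need the cause to be visible. Safety oversight runs at each site independently (8.12), across 11 sites (5.7), so an unnamed event may be classified differently from site to site.
- **Content of the SAE comparison.** Safety is a stated purpose of the trial (section 3). If 9.4.4 counts only its four listed events, the between-group SAE result omits a complication that the protocol itself calls possibly fatal.

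**Working it through.** The plan gives no pneumothorax rate and no precision target for it, so there is no figure of its own to reproduce. The check is a comparison of text, followed by simple binomial arithmetic.

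**Step 1. Where pneumothorax appears.**

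| Section | Purpose | Pneumothorax named? |
|---|---|---|
| 2.4.1 | Known risks | Yes, possibly fatal |
| 2.2.2 | Absolute contraindication | Yes, if untreated |
| 5.1, 5.2 | Eligibility | Yes, if untreated |
| 4.2.3, 8.1 | HBOT-related AEs (four events) | No |
| 9.4.4 | SAEs analysed (same four) | No |
| 8.12, 9.4.7.1 | Events for the 10/20/40 reviews (four events) | No |

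It is 0 of 4 on the review list and 0 of 4 on the HBOT-related/SAE list. Each list is the same wherever it is repeated.

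**Step 2. What would happen to a case.**

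- *Not serious:* documented under 8.6, included in the per-patient AE total of 4.2.3, and covered by the all-AE check at 10 patients. It is not on the named list at any of the three reviews.
- *Serious under 8.3, without ventilation, escalation of care or death:* recorded and reported as an SAE, and open to the general review by number and type. It is not on the named list. Its place in 9.4.4 depends on how that section is read.
- *Leading to ventilation, escalation of care or death:* counted at the reviews, but under that label. Its place in 9.4.4 again depends on the reading.

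**Step 3. The two readings of 9.4.4.** If its opening list defines the SAEs to be analysed, pneumothorax is out. If its next sentence, which counts each patient's total SAEs in hospital, governs, pneumothorax is in. Section 9.2 states the safety hypothesis for any severe adverse effect, and 4.2.3 promises totals of all AEs and SAEs. Both fit only the second reading. The terms add to the doubt: 4.2.3 and 9.4.4 expand SAE as severe, while 8.3 defines it as serious.

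**Step 4. What a named count could show.** The inputs are n = 10, 20 and 40 HBOT patients (9.4.7.1). With zero cases, the exact two-sided 95% upper limit is 1 − 0.025^(1/n):

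- n = 10: 1 − 0.025^(1/10) = 30.8%
- n = 20: 1 − 0.025^(1/20) = 16.8%
- n = 40: 1 − 0.025^(1/40) = 8.8%

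The one-sided 95% limits, 1 − 0.05^(1/n), are 25.9%, 13.9% and 7.2%.

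**Step 5. Is a case likely to arise?** The rates below are assumptions. The chance of at least one case is 1 − (1 − p)^n:

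| Assumed rate p | n = 10 | n = 20 | n = 40 |
|---|---|---|---|
| 1% | 9.6% | 18.2% | 33.1% |
| 2% | 18.3% | 33.2% | 55.4% |
| 5% | 40.1% | 64.2% | 87.1% |
| 10% | 65.1% | 87.8% | 98.5% |

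**The case against.** The strongest reply is that the lists do not limit what is collected or reviewed. All AEs are collected and documented (4.2.3, 8.6). A life-threatening event, one that prolongs the hospital stay or an important medical event is an SAE by definition (8.3). Sites report AEs and SAEs to the co-Principal Investigators, who meet every three weeks (8.12). The interim analysis at 10 patients covers all endpoints (9.4.7), and AE and SAE incidence is one of them. A newly developed exclusion criterion is a ground for ending participation, and the reason must be recorded (5.8, 5.9).

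This reply stands against two stronger inferences that a reader might draw. One is that a pneumothorax short of ventilation, escalation of care or death would never reach the safety review. The provisions above contradict that. The other is that the trial could then put no bound on the risk. That fails too, because a count could be drawn from the AE records whether or not the event is listed.

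Two further objections are fair. The zero-event limits would be the same for any adverse event at these sample sizes, so they measure the size of the trial and not the omission. And exclusion from 9.4.4 is one reading of ambiguous text, not an established fact.

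The reply does not supply a named tally. The general SAE wording specifies no event, the all-AE check is stated only for the pause at 10 patients, and the meetings at 10, 20 and 40 name only the four events.

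**Conclusion.** The point holds in a limited form. Pneumothorax is absent from all five places where the plan names safety events (4.2.3, 8.1, 8.12, 9.4.4, 9.4.7.1), although 2.4.1 says it can be fatal. It would be recorded and could come up in the general SAE review. It is not tallied as its own event at 10, 20 or 40 patients, and a case may be visible only as ventilation, escalation of care or death. Section 9.4.4 must be reconciled with 9.2 and 4.2.3, because on its literal reading the SAE comparison omits the event.

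No bias or power figure attaches to the omission. At assumed rates of 1% to 10%, the chance of at least one case among 40 HBOT patients is about 33% to 98%, so the gap could matter in practice. This should be corrected, but it does not mean that the safety review would miss the event altogether.

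**What to change.** 1. Add pneumothorax and other pulmonary barotrauma to the lists in 4.2.3, 8.1, 8.12, 9.4.4 and 9.4.7.1.
2. State in 9.4.4 that the between-group comparison counts all SAEs meeting the definition in 8.3, and tabulate the listed HBOT-related events separately.
3. At each review, report the number of detected pneumothorax cases in the HBOT group with an exact two-sided 95% interval.

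The cost is one item in five lists, a sentence or two in 9.4.4 and one line in each review report. As a protocol amendment it needs IRB approval (12.2). No new procedure is required, because imaging done during the hospital stay is already taken from the chart (7.1.2).

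There is a downside. That imaging is only what standard of care produced, and the entry check also relies on a clinically indicated X-ray (5.1). The count is therefore of detected cases, may understate the risk, and should be labelled so. None of this proposes a halting or treatment rule.

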#### **9.4.7.2 Efficacy Review**

In the interim analysis, we will also compute proportion of overall mortality along with proportion that needed ventilation. The statistician conducting the analysis will be blinded from the treatment assignment to ensure that the type 1 error of our power calculation for final analysis is preserved.

#### **9.4.8 Additional Sub-Group Analyses**

We will also compare our primary and secondary endpoints stratified by age groups and sex. However, because of small sample size these analyses will be exploratory and hypothesis generating rather than formal hypothesis testing. We will report effect estimates and their standard errors.

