## **5.7 Total Number of Participants and Sites**

There are a total number of 11 sites. All sites will submit their own individual IRB proposal to be approved by their respective institution's IRB. NYU is the lead site and the Co-Principal Investigators, [name] and [name], will be the lead coordinators of this study.

Recruitment will end when approximately 40 participants are enrolled in the HBOT group.

We will create a comparison cohort from chart review of 120 patients who received standard treatment and were matched with 40 HBOT patients in 3:1 ratio, such that the comparison group will consist of 120 standard of care patients. For this retrospective comparison group, we will be requesting a waiver of consent and authorization for this cohort.

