### 9.4 Description of Statistical Methods

#### 9.4.1 General Approach

We will summarize the continuous variables using mean, median, standard deviation and ranges, and the categorical variables using frequency and proportions. Variables will also be summarized graphically. Baseline characteristics of the participants who received HBOT will be compared with that of control patients receiving SOC. If we find any significant difference in the baseline variables between the two matched groups, we will adjust for them as covariates in outcome analysis. T-test or ANOVA will be used for continuous variables whereas chi-squared test will be used for comparison of proportions. All tests will be two tailed at significance level of 0.05. Appropriate transformations (such as log transformation) will be considered for any continuous variable that indicates non-normality. Statistical software R and SAS will be used for the analysis.

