#### **9.4.11 Exploratory Analyses**

Please see additional subgroup analysis.

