### **9.5 Sample Size**

Using a sample of 160 patients, 40 in HBOT arm and 120 in SOC arm (post matching) we can detect a reduction of 22.5% or higher, against the null of no difference, with 80% power at significance level of 0.05, assuming that the mortality rate in SOC arm is about 80%.

For the secondary analysis, our proposed sample of 160 patients will similarly allow us to detect a difference of 22.5% in need for ventilation between HBOT group and SOC group with 80% power. For comparing the continuous outcome of number of days in ventilation, we have 80% power to detect effect size (cohen's d) of 0.51 with 160 patients.

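### Section 9.4.8 plans exploratory HBOT effects within age groups and by sex, but no estimate of whether the effect differs between those groups

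*Combined protocol and SAP*

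**What the plan says.** Section 9.4.8 (Additional Sub-Group Analyses) states: "We will also compare our primary and secondary endpoints stratified by age groups and sex". It then says that, because the sample is small, these analyses are exploratory and meant to suggest hypotheses, with no formal testing. It ends: "We will report effect estimates and their standard errors".

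Neither the number of age groups nor their cut-points are given. No interaction term, between-stratum contrast or heterogeneity measure is named in 9.4.8. Nothing elsewhere fills the gap:

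- 9.4.2 and 9.4.3 use regression only to adjust for baseline confounders.
- 9.4.9 (multiplicity) is marked not applicable.
- 9.4.11 (Exploratory Analyses) reads, in full, "Please see additional subgroup analysis", so 9.4.8 is the whole exploratory plan.
- 9.1 leaves the formal SAP to the end of a study that is not blinded.

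**The concern.** The one thing a subgroup analysis can add to the overall comparison is a suggestion that the effect of HBOT varies with age or sex. The estimate that bears on this is the difference between stratum effects, with its own uncertainty. Separate stratum estimates with separate standard errors leave the reader to judge that difference by eye, and the standard error of each stratum is smaller than the standard error of the difference. With 40 HBOT patients divided among strata, chance differences will be large, and some could be carried forward as hypotheses for later trials.

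The undefined age groups add to this. Because the formal SAP is due only at the end of an unblinded study, cut-points could be chosen after outcomes are known.

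**Working it through.** **Inputs from the plan.** 40 HBOT and 120 SOC patients (9.5), "matched with 40 HBOT patients in 3:1 ratio" (5.7). SOC rate 80%, and "we can detect a reduction of 22.5% or higher, against the null of no difference, with 80% power at significance level of 0.05" (9.5), read as an absolute fall to 57.5%. Two-sided 0.05 (9.4.1). Section 9.4.2 attaches the 80% to mechanical ventilation where 9.5 attaches it to mortality; the arithmetic below is the same for either.

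**Inputs assumed.** Stratum sizes are not in the plan. For two strata I use HBOT splits of 20/20, 24/16, 28/12 and 30/10, and for three age groups 13/13/14 or 13/13/13. SOC is three times HBOT in each stratum, which is reasonable because 9.3 matches on age and gender. Patients are treated as independent, as in the plan's own chi-squared test.

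**Step 1: the plan's own figure.** The pooled rate is (40×0.575 + 120×0.80)/160 = 0.744.

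- Null SE = √[0.744×0.256×(1/40 + 1/120)] = 0.0797
- Alternative SE = √[0.575×0.425/40 + 0.80×0.20/120] = 0.0863
- Power = Φ[(0.225 − 1.96×0.0797)/0.0863] = 78.7%

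This agrees with the stated 80% to within 2 points. No figure is stated for subgroups.

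**Step 2: SE of one stratum effect.** For n HBOT and 3n SOC patients, variance = 0.575×0.425/n + 0.80×0.20/(3n). With n = 20 this is 0.01222 + 0.00267 = 0.01489, so SE = 0.122.

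**Step 3: SE of the contrast.** It is the square root of the sum of the two stratum variances. For 20/20 this is √(0.01489 + 0.01489) = 0.1725.

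**Step 4: consequences when the true effect is 22.5 points in both strata.** The 95% half-width is 1.96×SE. The chance of a gap above 20 points is 2×[1 − Φ(0.20/SE)]. The mean absolute gap is SE×√(2/π). Power for a true interaction of 22.5 points is approximately Φ(0.225/SE − 1.96), keeping the same variances.

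| HBOT split | SE of contrast (points) | 95% half-width (points) | Chance of gap above 20 points | Mean absolute gap (points) | Power for a 22.5-point interaction |
|---|---|---|---|---|---|
| 20/20 | 17.3 | 33.8 | 24.6% | 13.8 | 25.6% |
| 24/16 | 17.6 | 34.5 | 25.6% | 14.1 | 24.8% |
| 28/12 | 18.8 | 36.9 | 28.8% | 15.0 | 22.2% |
| 30/10 | 19.9 | 39.0 | 31.5% | 15.9 | 20.3% |

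A binomial simulation of 400,000 studies gives 24.6% for 20/20 and 28.9% for 28/12, in agreement. If HBOT has no effect anywhere (80% v 80%), the chance of a gap above 20 points is 17.1% (20/20) to 23.6% (30/10).

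**Step 5: three age groups.** By simulation with the uniform 22.5-point effect, the largest minus the smallest stratum effect averages about 25 points. It reaches 20 points or more in 62% of studies with 13/13/14 HBOT patients and 64% with 13/13/13.

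**The case against.** The strongest reply is that 9.4.8 already says what a cautious statistician would want: the sample is small, the analyses are exploratory, nothing is formally tested, and standard errors will be shown. This stands as a partial safeguard, and it is why the point is minor. It does not tell the reader how uncertain a difference between strata is.

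Three stronger readings are tempting, and the documents do not support them.

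- A reader might infer that the plan means to compare stratum effects with one another and claim a differential effect. Section 9.4.8 describes HBOT v SOC within strata and says neither thing.
- A reader might count how often one stratum would be significant and the other not. For two equal strata with power 0.513 each, that is 2×0.513×0.487 = 50%. But this uses per-stratum testing, which the section disclaims, and it depends on a true 22.5-point effect; with no effect the figure is about 9%.
- A reader might infer that apparent heterogeneity will usually appear. On a 20-point threshold, itself a choice, that fits only the assumed three age groups. For sex, about three studies in four fall below it when the split is even.

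It is also fair to say that the contrast between the sexes can be derived from the promised output, as √(0.122² + 0.122²) = 0.173. A reader should not have to do that, and with three or more age groups no single difference suffices. Finally, the added estimate will be too imprecise to establish a realistic interaction. That is so, and its width is the useful message.

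**Conclusion.** The point holds as a minor gap in analysis and reporting. The plan's only exploratory analysis omits the estimate that addresses its own question, and it leaves the age groups undefined until after outcomes may be known. Under a uniform effect of 80% v 57.5%, chance alone separates two strata by 20 points or more in about 25% to 31% of studies, and spreads three age groups that far in about 62 to 64%. These figures rest on the plan's assumed rates, on 3:1 SOC to HBOT in each stratum, and on stratum sizes and a number of age groups that the plan does not give. The overall efficacy and safety analyses do not depend on 9.4.8, so nothing in them changes.

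**What to change.** In 9.4.8, keep the stratum estimates and add three things:

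1. For each endpoint, report the HBOT-by-sex and HBOT-by-age contrast with a 95% confidence interval. Enter age as continuous, or fix the cut-points in writing before outcomes are reviewed.
2. State the scale. The logistic model of 9.4.2 gives a ratio of odds ratios, while the working here uses risk differences. If SOC mortality varies with age, a uniform effect on one scale is not uniform on the other.
3. State that no differential effect will be inferred from stratum estimates alone.

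The cost is a few model terms and a sentence or two, with no new data. Continuous age brings a linearity assumption. The interval will be wide (about ±34 to 39 points on the risk-difference scale for two strata), with only about 20 to 26% power for a 22.5-point interaction, so the text should present it as a display of uncertainty and not as a test.
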